**South Texas Early Prevention Studies PreK**

**Study Design and Protocol**

**September 28, 2018**

## **Study Design and Participants**

The STEPS-PreK4 was a CRT where preschools, embedded within elementary schools, were the unit of randomization, intervention, and analysis. The study was designed for two years of intervention (pre-kinder to kindergarten) and four data collection periods (fall 2018, spring 2019, fall 2019, and spring 2020). Due to the COVID-19 pandemic the study was stopped prematurely and only results from the first three periods will be presented.

The two school districts where the study was conducted are located along the Texas-Mexico border in the county of Hidalgo. These school districts were selected because of the high poverty and health risk-factors levels. The preschools have two grade levels with children 3 and 4 years of age. The present study targeted preschools with children 4 years of age. Demographics of the two school districts were similar, 99% Hispanic, 92% economically disadvantaged, and 42% identified as English as a second language.

## **Intervention**

The BN CHSP is a Texas Education Agency (TEA)-approved CSHP. This health program was first piloted in schools located in low-income neighborhoods where enrollment was predominantly Black and Latino children. For this reason, the curricula were given the name Bienestar/NEEMA. *Bienestar* and *NEEMA* mean well-being in Spanish and Swahili, respectively. TEA-approved CSHP aims is to control and prevent childhood obesity, youth-onset type 2 diabetes, and cardiovascular disease by providing instruction in health, nutrition, physical education, and chronic disease knowledge across several environments.

The Social-Ecological Model guided the BN CSHP design. This theory postulates that health behaviors are molded by individual, interpersonal, and environmental interactions. Thus, BN CSHP encompasses curricula from preschool to eighth grade and is designed to target the four environments that influence children's health behaviors: 1) *Healthy Lifestyles Healthy Minds* (Health), 2) *Moving For Life* (Physical Education), 3) *Eat to Live* (Child Nutrition/School Food Service), and 4) *MyFamily/MiFamilia* (Home). **Table 1** shows the preschool health education components of both treatment arms.

## **Measures**

*Household characteristics.* Family Demographic and Household Health Characteristic questionnaires were sent to parents/guardians through 4 modes: online, face-to-face, school parent liaisons, and children. English and Spanish questionnaires collected information on age, gender, race/ethnicity, educational attainment, household income, persons living per household, physical activity, sedentary lifestyles, and family (1st and 2nd degree) history of hypertension and diabetes.

*PACER Fitness Test.* The PACER fitness test is a multistage shuttle run designed to measure CRF. The objective of the PACER is to run as long as possible while keeping a specified pace. Children run back and forth across a 20-meter course at a tempo that gets faster each minute paced by an audio signal. For this study, the PACER test was

adapted for preschool children by adjusting the course to a 15-meter distance and using a 20-meter cadence. The test begins at a slow pace and each minute the pace increases. Beeps on the soundtrack indicate when a student should reach one end of the course where they stop and wait for the next beep. Children continue running until the pace can no longer be sustained for two laps. As soon as children stop running, their number of laps are recorded.

### **Sample Size Calculation**

The sample size for the primary endpoint, obesity prevalence, assumed a 5% obesity rate decrease in the intervention compared to control group, a SD of 1.4, an intra-cluster correlation coefficient of 0.01, 70% response rate, and an attrition rate of 16 percent. [source: LJ ISD, PSJA ISD] A total of 28 preschools (clusters) with a mean cluster size of 49 children per school was estimated to detect the effect size with 80% power at a significant level of  $\alpha = 0.05$ . The calculated sample size was enough for a difference of at least 4.5 laps between treatments (secondary outcome) and the statistical power was 82% for alpha 0.05 with sample size of 40 children per cluster.

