**South Texas Early Prevention Studies PreK**

**Study Design and Protocol**

**September 28, 2018**

## **Statistical Analyses**

Summary statistics are presented as means (standard deviations; S.D.), and frequencies (percentages) to describe the treatment groups, and p-values adjusted by random factors. The primary aim of this report was to assess the longitudinal effect of the BN CSHP on the CRF of children as compared to a control group. The CRF was measured by the number of laps in the PACER fitness test. The counts of laps were positively skewed and assumed to follow a Poisson probability distribution. The linear fixed predictors of the average number of laps were time (continuous variable consisting of the periods of data collection), treatment effect (discrete factor with control group as the reference level), and their interaction (the nested district-level, school-level, and classroom-level to account for random intercepts).

A generalized linear mixed model (GLMM) with a natural logarithm link and a Poisson probability distribution was fitted to the data using the R package lme4, version 1.1-27.1. Upon detecting a significant overdispersion, a GLMM with a negative binomial distribution was used instead to assess the unadjusted and adjusted effect of the intervention and to obtain 95% confidence intervals (CI).

The models were adjusted for covariates sex, age, body mass index (BMI), education level of caretaker who responded to the demographic survey, household income to poverty ratio (IPR), time watching T.V., time playing with electronic devices, hours of sleep at night, and time exercising outside school. The interactions between period and treatment by BMI, sex, and age were also included in the full model. As suggested by Brown all continuous variables were transformed to a unit-scale and used the Bound Optimization BY Quadratic Approximation optimizer in the lme4 package to ensure convergence. The analysis was performed in R version 4.1.0 [R Core Team, 2013].

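### The 80% power for obesity prevalence rests on an SD of 1.4, impossible for a yes/no endpoint, and cannot be reproduced because the control prevalence and the scale of the 5% are not stated

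*Protocol*

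**What the plan says.** The Protocol, under Sample Size Calculation, names what is being sized: "The sample size for the primary endpoint, obesity prevalence". It says the calculation "assumed a 5% obesity rate decrease in the intervention compared to control group, a SD of 1.4, an intra-cluster correlation coefficient of 0.01". It adds a "70% response rate, and an attrition rate of 16 percent. [source: LJ ISD, PSJA ISD", the bracket being the source given for the assumptions. The result is "A total of 28 preschools (clusters) with a mean cluster size of 49 children per school", for 80% power at a significance level of 0.05.

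The same paragraph covers the secondary outcome, PACER laps: for a difference of at least 4.5 laps, "the statistical power was 82% for alpha 0.05 with sample size of 40 children per cluster".

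Neither document gives the obesity prevalence expected in control schools or names the variable or unit of the SD. Neither gives the scale of the 5%, the sidedness of the test or the allocation ratio. Neither says whether 49 per school is before or after non-response and attrition.

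**The concern.** A child is obese or not, so the child-level SD is √(p(1−p)), which is at most 0.5. An SD of 1.4 must belong to some other measure, and none is named. The quantity that fixes the variance of a proportion, its prevalence, is missing.

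This paragraph is the only justification of sample size for the endpoint the Protocol calls primary. Without a valid variance input, a reader cannot tell what difference in obesity 28 schools could detect. An obesity result, null or not, then cannot be weighed against the stated 80%. The lap analysis in the SAP does not depend on this calculation.

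**Working it through.** **Inputs from the Protocol (Sample Size Calculation).** 28 schools in total, mean 49 children, ICC 0.01, attrition 16%, response 70%, α = 0.05, difference 5%, SD 1.4, claimed power 80%.

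**Assumed, because not stated.** 14 schools per arm, a two-sided test, comparison at a single time point, and control prevalence p₁ from 10% to 30%.

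**Effective sample size per arm**, 14m / (1 + (m − 1) × 0.01):
- m = 49: design effect 1.48; 14 × 49 / 1.48 = 463.5.
- m = 49 × 0.84 = 41.16 (after attrition): design effect 1.4016; effective n = 411.1.

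The second reading is suggested, not proved, by the 40 per cluster used for laps, which is close to 41.

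**Step 1: the plan's figure from its own inputs.** Power = Φ(δ / (SD × √(2/n)) − 1.96).
- δ = 0.05, SD = 1.4, n = 463.5: standard error 1.4 × √(2/463.5) = 0.092; Φ(0.54 − 1.96) = 8%.
- δ = 5 in the same units: about 100%.
- 1.4 as a school-level SD in percentage points, 5-point fall, 14 schools per arm: about 100%.
- Difference detectable with 80% power at SD 1.4: 2.80 × 0.092 = 0.26 units (0.27 with 41), which matches 5% on neither scale.
- Largest common SD that gives 80% for a 0.05 difference: 0.05 / (2.80 × √(2/n)) = 0.27 with 49 and 0.26 with 41.

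None of these returns 80%. The SD does not fit the lap statement either. With 40 per cluster and the same ICC and allocation, 82% power for 4.5 laps implies an SD of about 22; an SD of 1.4 would give about 100%.

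**Step 2: binomial variance, 5-point absolute fall.** Power = Φ(0.05 / √((p₁q₁ + p₂q₂)/n) − 1.96), with p₂ = p₁ − 0.05 and q = 1 − p. Example at p₁ = 20%, m = 49: √((0.16 + 0.1275)/463.5) = 0.0249; Φ(2.008 − 1.96) = 52%. The detectable difference d solves d = 2.80 × √((p₁q₁ + p₂q₂)/n) with p₂ = p₁ − d.

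| Assumed control prevalence | Power, 49 analysed | Detectable difference (points), 49 | Power, 41 analysed | Detectable difference (points), 41 |
|---|---|---|---|---|
| 10% | 83% | 4.85 | 78% | 5.11 |
| 15% | 64% | 5.96 | 58% | 6.29 |
| 20% | 52% | 6.82 | 47% | 7.20 |
| 25% | 45% | 7.50 | 41% | 7.93 |
| 30% | 40% | 8.04 | 36% | 8.50 |

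Power reaches 80% up to a control prevalence of about 10.6% (49) or 9.6% (41).

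**Step 3: other readings.**
- One-sided test (1.645 for 1.96): 80% holds up to 13.0% (49) or 11.7% (41).
- Baseline adjustment, standard error multiplied by √(1 − r²), at 20% prevalence with assumed r = 0.5/0.6/0.7: 64/71/80% (49) or 59/66/75% (41).
- A 5% relative fall: under 10% power at prevalences of 10% to 35%.
- Both losses applied to the 49 (49 × 0.70 × 0.84 = 28.8 analysed): the two-sided limit for 80% drops to about 7.8%.

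**The case against.** The strongest reply is that the SD may never have entered the obesity calculation. An ordinary two-proportion calculation for a fall from 10% to 5% needs 435 children per arm before clustering. Then 435 × 1.48 / 49 = 13.1, so 14 schools per arm and exactly 28 in total. Power by that method is 82.5%, or 79.8% with a t test on 26 degrees of freedom. On this view the figure is undocumented rather than wrong. It stands that 80% is attainable at some prevalence. But the 10% is in neither document, and the paragraph lists the SD among the assumptions of the obesity calculation. As written, a stated input is impossible.

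It is also fair that the sizes above depend on supplied assumptions. The trial planned "four data collection periods (fall 2018, spring 2019, fall 2019, and spring 2020", so a single-time-point comparison may not be the intended analysis, and a baseline correlation of 0.7 would restore 80% at 20% prevalence with 49 analysed. Nothing states that 49 becomes 41. The table is therefore a conditional range, not an estimate of true power.

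Finally, the trial stopped early and the SAP concerns fitness: "The primary aim of this report was to assess the longitudinal effect of the BN CSHP on the CRF of children". The number of schools can no longer change, and the confidence interval of any obesity result would show which differences fit the data. This limits the consequence to the obesity endpoint. It does not support the 80%, which remains the public justification for the endpoint named primary.

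**Conclusion.** The concern holds. An SD of 1.4 is impossible for obesity status at any prevalence, whatever else is assumed, and no direct reading of the printed inputs gives 80% power. The missing inputs decide the answer. For a 5-point absolute fall, two-sided, 14 schools per arm and no baseline adjustment, power is 83% to 40% with 49 analysed, or 78% to 36% with 41, as the assumed control prevalence goes from 10% to 30%. If the 5% is relative, power is under 10% at prevalences of 10% to 35%. True power has not been shown to be below 80%: a control prevalence near 10%, or a strong baseline correlation, would support the claim. The stated figure cannot be verified and carries an invalid input.

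**What to change.** Replace the paragraph with a two-proportion calculation for a cluster-randomised trial:

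- Remove the SD of 1.4. If it belongs to a continuous measure, name that measure as the one powered.
- State the control prevalence and its source, whether 5% is absolute or relative, the sidedness, the allocation, and whether baseline is adjusted for.
- Say whether 49 is enrolled or analysed, and how the 70% response and 16% attrition enter.
- Restate the power, or the detectable difference, for 28 schools at the analysed cluster size. As an illustration only, at an assumed 20% prevalence the detectable difference is about 6.8 points with 49 analysed or 7.2 with 41.

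The cost is one rewritten paragraph. The inputs should come from the district data already cited; if those do not include obesity prevalence, the rate and its source must be added. The design does not change and no schools are added, because the fix restates what the 28 schools can detect. The restated figure may be less favourable than 80%.

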**South Texas Early Prevention Studies PreK**

**Study Design and Protocol**

**September 28, 2018**

## **Statistical Analyses**

Summary statistics are presented as means (standard deviations; S.D.), and frequencies (percentages) to describe the treatment groups, and p-values adjusted by random factors. The primary aim of this report was to assess the longitudinal effect of the BN CSHP on the CRF of children as compared to a control group. The CRF was measured by the number of laps in the PACER fitness test. The counts of laps were positively skewed and assumed to follow a Poisson probability distribution. The linear fixed predictors of the average number of laps were time (continuous variable consisting of the periods of data collection), treatment effect (discrete factor with control group as the reference level), and their interaction (the nested district-level, school-level, and classroom-level to account for random intercepts).

A generalized linear mixed model (GLMM) with a natural logarithm link and a Poisson probability distribution was fitted to the data using the R package lme4, version 1.1-27.1. Upon detecting a significant overdispersion, a GLMM with a negative binomial distribution was used instead to assess the unadjusted and adjusted effect of the intervention and to obtain 95% confidence intervals (CI).

The models were adjusted for covariates sex, age, body mass index (BMI), education level of caretaker who responded to the demographic survey, household income to poverty ratio (IPR), time watching T.V., time playing with electronic devices, hours of sleep at night, and time exercising outside school. The interactions between period and treatment by BMI, sex, and age were also included in the full model. As suggested by Brown all continuous variables were transformed to a unit-scale and used the Bound Optimization BY Quadratic Approximation optimizer in the lme4 package to ensure convergence. The analysis was performed in R version 4.1.0 [R Core Team, 2013].

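### With three periods left, the SAP's single treatment-by-time slope cannot separate an end-of-pre-K effect that fades from no effect; a supplementary fit with period as a factor would

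*SAP*

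**What the plan says.** The SAP (Statistical Analyses) states its purpose as follows: "The primary aim of this report was to assess the longitudinal effect of the BN CSHP on the CRF of children". The fixed predictors of the lap count are "time (continuous variable consisting of the periods of data collection"), then "treatment effect (discrete factor with control group as the reference level), and their interaction". The link is logarithmic, the distribution is negative binomial once overdispersion is found, and there are nested random intercepts for district, school and classroom. The SAP adds that "all continuous variables were transformed to a unit-scale", and, for the adjusted model, "The interactions between period and treatment by BMI, sex, and age were also included in the full model".

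The Protocol (Study Design and Participants) planned "two years of intervention (pre-kinder to kindergarten) and four data collection periods (fall 2018, spring 2019, fall 2019, and spring 2020"). After the early stop, "only results from the first three periods will be presented".

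The documents do not give the numeric codes for the periods, whether scaling includes centring, how classrooms are identified after the move to kindergarten, or which coefficient carries the conclusion. No period-specific contrast and no check of linearity is described.

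**The concern.** The interaction is the natural carrier of a longitudinal effect, although the SAP does not name it as the test. A straight line through three periods allows one trajectory shape only: the change in the arm difference by spring 2019 is a fixed fraction of the change by fall 2019.

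The early stop makes this matter more. Spring 2020 is lost, so spring 2019 is the only assessment at the end of a school year and the only follow-up before kindergarten. If the programme raised fitness by the end of pre-K and the gain was not kept, the linear term alone would not tell the reader so. Laps is the outcome of the SAP's stated primary aim.

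**Working it through.** The documents give no figure for period weights, so there is nothing of theirs to reproduce.

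**1. Slope weights, equally spaced codes.** For codes t and information n per period, the slope gives each period's log arm ratio the weight n(t − t̄)/Σn(t − t̄)², with t̄ the n-weighted mean.
- Balanced, t = 0, 1, 2: t̄ = 1 and the denominator is 2. Weights −0.5, 0, +0.5.
- Assumed retention 1, 0.92, 0.84 (the Protocol's 16% attrition, taken as reached by fall 2019): t̄ = 2.60/2.76 = 0.942, denominator 1.831. Weights −0.515, +0.029, +0.485.
- Four planned periods, balanced: −0.3, −0.1, +0.1, +0.3. The exact zero arises from stopping at three.

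A linear rescaling of time leaves the relative weights unchanged. Random intercepts shared by all three periods leave the balanced zero unchanged.

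**2. Calendar coding.** With assumed months 0, 8, 12, t̄ = 6.667 and the denominator is 74.67. Weights −0.0893, +0.0179, +0.0714, so spring 2019 has 0.0179/0.0714 = 0.25 of fall 2019's weight.

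**3. New classroom identifiers in fall 2019.** Generalised least squares weights are (X′V⁻¹X)⁻¹X′V⁻¹. Assumptions: codes 0, 1, 2, three classrooms of 16 children per school, school variance share 0.01, balanced data.

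| Classroom share (assumed) | Spring 2019 weight | Fall 2019 weight | Ratio |
|---|---|---|---|
| 0.01 | 0.052 | 0.474 | 0.11 |
| 0.03 | 0.143 | 0.429 | 0.33 |
| 0.05 | 0.221 | 0.390 | 0.57 |

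**4. What one slope can express.** Relative to fall 2018, the fitted log ratio is 1 × slope in spring 2019 and 2 × slope in fall 2019, so spring is always half of fall. With months 0, 8, 12 it is always 8/12. This holds whatever the weights. At the 0.05 classroom share, a spring-only log ratio of 0.2 gives a slope of 0.221 × 0.2 = 0.044 and hence a fitted fall 2019 change of 0.088, where the true change is 0. More weight on spring therefore does not reveal a fade.

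**5. A spring-only gain on the lap scale.** Take 4.5 laps (the Protocol's difference) in spring 2019 only, with a flat control mean of 15 and balanced data. Treated means are 15, 19.5, 15, and the true spring ratio is 19.5/15 = 1.30. A constant fitted mean of 16.5 leaves residuals −1.5, +3, −1.5. These sum to 0, and weighted by t they give 3 − 3 = 0, so both score equations are solved. The interaction ratio is 1.00 and the fitted arm ratio is 16.5/15 = 1.10 at every period, including fall 2018, where the truth is 1.00. At a control mean of 10 the fitted ratio is 11.5/10 = 1.15.

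The expected score equations of a negative binomial log-link model without random effects were then solved for dispersion 0.5, 1, 2 and 5. Control means were flat at 10, 12, 15 or 20, or rising (10/12/14, 10/15/20, 15/18/21, 20/22/24).

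| Quantity | Equal codes, balanced | Equal codes, 16% attrition |
|---|---|---|
| True spring ratio | 1.20–1.45 | 1.20–1.45 |
| Interaction per period | 0.992–1.000 | 1.001–1.013 |
| Fitted fall 2018 ratio | 1.069–1.150 | 1.062–1.136 |

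With months 0, 8, 12, over both retention patterns, the interaction over 12 months is 1.04–1.12 and the fitted fall 2018 ratio 1.04–1.09.

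**6. Early and late onset.** True log ratios 0, 0.2, 0.2 and 0, 0, 0.2 give slopes of 0.094–0.101 and 0.099–0.105 per period (assumed control means 8/10/12 and 5/10/15). The linear model cannot separate these two patterns either.

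**The case against.** A reader might infer that the SAP's model discards spring 2019. The documents do not support that. Zero weight concerns the interaction only, and it needs equal spacing, balanced information and classroom labels that persist into kindergarten. The SAP's random classroom intercepts matter here: with new labels the spring weight can exceed half of fall 2019's. This limits the claim about weight but leaves the restriction on shape untouched.

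A reader might also infer that a spring-only gain must pass for baseline imbalance. That reading applies if time is uncentred with fall 2018 coded 0, or to the fitted fall 2018 values. If unit-scaling includes centring, the treatment coefficient is the arm ratio at mean time, and the same gain would appear there as an average treatment effect.

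Three further points are fair. A steadily accumulating effect is a defensible model for a two-year programme. The documents contain no evidence that any effect fades. The Protocol's sample-size section calls laps a secondary outcome, and the SAP is written in the past tense, so any added contrast comes after the fact. These points argue for a supplementary analysis, not for replacing the specified term.

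**Conclusion.** The point holds as a limit on what the specified analysis can show. Under any coding, one treatment-by-time slope over three periods ties spring 2019 to a fixed fraction of fall 2019, and no other contrast is planned. Under equal spacing, stable classroom labels and the assumed lap means, a spring ratio of 1.20–1.45 that is lost by fall 2019 leaves an interaction of about 0.99–1.01 per period and a fitted fall 2018 ratio of 1.06–1.15. Month coding or relabelled classrooms change these sizes but not the restriction. Lap means, dispersion, retention by period, months, classroom numbers and variance shares are all assumptions; the documents give none of them apart from the overall 16% attrition.

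Two stronger readings fail. Nothing here shows that the linear term is wrong or that an effect was missed. Nor does it show that the Protocol's power statement, "the statistical power was 82% for alpha 0.05 with sample size of 40 children per cluster", is in error: the Protocol attaches it to a 4.5-lap difference between arms and does not attribute it to the interaction. Power for the interaction itself cannot be derived, because no lap SD and no intra-cluster correlation for laps is given.

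**What to change.** Keep the specified linear term. Add one refit with the same negative binomial distribution, random effects and covariates, but with period as a three-level factor. Contrasts taken from the linear fit would not serve, since they are multiples of one slope. Report treatment-by-period rate ratios with 95% CI for spring 2019 and for fall 2019, each against fall 2018, labelled as a supplementary analysis.

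State the numeric period codes, whether time is centred, and how classrooms are identified in fall 2019. For the full model, say whether the period interactions with BMI, sex and age stay linear in time.

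The cost is one more fit to the same data, with two extra parameters if those covariate interactions stay linear and more if they are recoded. It adds a second contrast to interpret. If the effect truly grows linearly, the joint 2-df test has less power than the linear term; the size of that loss depends on the lap SD and intra-cluster correlation, which the documents do not give. No new data are needed.

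### The lap model leaves the arms free to differ in fall 2018 and has no child-level term, so its treatment-by-time slope is unbiased but less precise than the collected data allow

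*SAP*

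**What the plan says.** The SAP (Statistical Analyses) states its purpose as follows: "The primary aim of this report was to assess the longitudinal effect of the BN CSHP on the CRF of children". The outcome is a lap count: "The CRF was measured by the number of laps in the PACER fitness test". The fixed effects are "time (continuous variable consisting of the periods of data collection", then "treatment effect (discrete factor with control group as the reference level), and their interaction". The random part is "the nested district-level, school-level, and classroom-level to account for random intercepts". No child-level term is described.

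The covariate sentence begins "The models were adjusted for covariates sex, age, body mass index (BMI), education level of caretaker who responded to the demographic survey" and goes on to five more: income-to-poverty ratio, television time, device time, sleep and exercise outside school. That makes nine, and fall 2018 laps are not among them.

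The Protocol (Study Design and Participants) plans "four data collection periods (fall 2018, spring 2019, fall 2019, and spring 2020" and says that, after the early stop, "only results from the first three periods will be presented". The rows analysed are thus fall 2018, spring 2019 and fall 2019. Preschools are the randomised units, and the Sample Size Calculation gives 28 of them.

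**The concern.** If fall 2018 was measured before the programme could act, randomisation makes the two arms equal in expectation at that point. The planned model does not use this. Its treatment main effect estimates an arm difference at the start, and the interaction then measures change from it. Any chance difference in fall 2018 is subtracted in full, together with its noise. With 28 randomised schools, some chance difference is to be expected.

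The model also has no means of linking a child's later laps to that child's own starting laps: they are not a covariate, and no child intercept ties the rows together. What is at stake is precision in a trial that has already lost its fourth measurement.

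**Working it through.** **The plan's own figure.** The Protocol states 82% power for a 4.5-lap difference with 40 children per cluster. It gives no SD for laps, so this cannot be reproduced. That is a separate matter, because the variance ratios below do not need an SD.

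**Inputs.** From the Protocol: 28 schools, 40 children per school, ICC 0.01 (stated for obesity). Assumed: a 14:14 split, ICC 0.05 as an alternative, correlation of true school levels between periods 0.8, child-level correlation r of 0.4 to 0.7, three complete and equally spaced periods, equal correlation between periods, linear scale.

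**Step 1: the planned contrast.** With three equally spaced, complete periods, the middle one drops out of a linear slope, which becomes (fall 2019 − fall 2018)/2. In units of the school-mean variance, the fall 2019 contrast has variance 2(1 − ρ), where ρ is the between-period correlation of school means.

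**Step 2: ρ.** V = ICC + (1 − ICC)/40; C = 0.8·ICC + r(1 − ICC)/40; ρ = C/V. For ICC 0.01 and r = 0.4: V = 0.03475, C = 0.008 + 0.0099 = 0.0179, ρ = 0.515.

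**Step 3: using fall 2018 as baseline.**
- As a covariate, with one fall 2019 contrast: variance 1 − ρ², ratio to the plan (1 + ρ)/2.
- Common fall 2018 mean, linear slope kept: given fall 2018, the two follow-ups have covariance (1 − ρ)[[1 + ρ, ρ], [ρ, 1 + ρ]] and effects in proportion ½ : 1. The variance is (1 − ρ)(1 + 2ρ)/(1.25 + 0.25ρ), and the ratio to the plan is (1 + 2ρ)/(2.5 + 0.5ρ).

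**Step 4: one effect averaged over both follow-ups.** If the effect builds linearly, the average is 0.75 of the fall 2019 effect. Its variance is (1 − ρ)(1 + 2ρ)/2, so its information relative to the plan is 2.25/(1 + 2ρ), which is a gain only for ρ below 0.625.

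| ICC | r | ρ | Variance ratio, covariate | Variance ratio, common mean | SE ratio, common mean | Information, averaged effect |
|---|---|---|---|---|---|---|
| 0.01 | 0.4 | 0.515 | 0.758 | 0.736 | 0.858 | 1.11 |
| 0.01 | 0.7 | 0.729 | 0.864 | 0.858 | 0.926 | 0.92 |
| 0.05 | 0.4 | 0.671 | 0.836 | 0.826 | 0.909 | 0.96 |
| 0.05 | 0.7 | 0.768 | 0.884 | 0.879 | 0.938 | 0.89 |

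An effect with 80% power under the planned slope would have about 85% to 90% with the common mean. With the averaged effect it would have 84%, 76%, 78% and 75% in the four rows, a loss in three of them.

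**Step 5: stable schools.** At ICC 0.10, perfectly stable school levels and child-level correlation 0.3 to 0.7, ρ is 0.871 to 0.945. The covariate ratio is then 0.936 to 0.972, a gain of 3% to 6% of variance.

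**Step 6: simulation.** On the linear scale, with 28 schools of 40 and the cost of estimating the baseline slope included, the covariate ratio was 0.79 to 0.92. For overdispersed counts analysed as log school means, over a wider set of correlations, it was 0.65 to 0.93, with no bias in either estimator.

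**The case against.** The strongest reply is that nothing here is invalid. Both analyses estimate the effect without bias under randomisation, and the treatment-by-time term answers the stated longitudinal aim directly. This stands. A reader might infer that regression to the mean biases the planned slope. It does not in expectation. The slope is correlated with the chance fall 2018 difference, at −√((1 − ρ)/2), which is −0.49 at ρ = 0.515 and −0.34 at ρ = 0.768, but over repeated randomisations this is variance, not bias.

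Second, the obvious remedy can do harm. A follow-up model with a single treatment effect over spring and fall 2019 changes the estimand and can lose power (step 4). This stands and shapes the fix.

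Third, 2(1 − ρ) is not the variance that the planned model would report. Treating a child's rows as independent, it would use about 2(1 − ICC)/40 per school. At ICC 0.01 that is 0.0495, against a true 2(V − C) of 0.0337 (r = 0.4) or 0.01885 (r = 0.7), so the reported SE is about 1.2 to 1.6 times the true one. At ICC 0.05 the same arithmetic gives about 1.0 to 1.2. This also stands: the missing child term is part of the problem and must be part of the remedy.

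Fourth, the documents neither call fall 2018 a baseline nor say that it preceded delivery. If delivery had begun, conditioning on fall 2018 could remove part of the effect. Its place as the first period of a two-year programme makes a pre-programme measurement plausible, but the sponsor has to confirm it.

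**Conclusion.** The point holds as one of efficiency. The direction follows from the model as written, for any between-period correlation below 1, provided fall 2018 is pre-programme. The size is not in the documents. With school-mean correlations of about 0.5 to 0.8, the variance is about 0.74 to 0.88 of the planned contrast's (SE 6% to 14% smaller). With very stable school means the gain is only a few percent.

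These figures are a linear, complete-data approximation on school means, not a prediction of the interval that the fitted count model will report. In particular, the assumed 0.8 lets school levels shift between periods, which random intercepts alone do not describe.

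A reader might turn the ratios into a fixed saving, since 1/0.88 to 1/0.74 looks like 14% to 35% more schools at no cost. The documents do not support that: they state no correlation, and their only ICC is for obesity.

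**What to change.** Confirm and state in the SAP whether fall 2018 laps were measured before the programme was delivered. If they were:

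- Keep the treatment-by-time term as the effect of interest.
- Code fall 2018 as time zero and preserve that zero when continuous variables are rescaled.
- Drop the free treatment main effect, so that the arms share a fall 2018 mean. In the full model, also drop any treatment-by-covariate term that does not involve time, since it would reopen a difference at fall 2018.
- Add a child random intercept to those for district, school and classroom. Children without a fall 2018 value stay in the analysis.

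An acceptable alternative is a follow-up model with child-level and school-mean fall 2018 laps as covariates, a child random intercept and a treatment-by-period term, so that the fall 2019 effect is estimated specifically. Do not use a single effect averaged over spring and fall 2019.

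Report the current model alongside. The SAP is written in the past tense and describes overdispersion as already found. If laps have been analysed, label the new model as added afterwards.

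The cost is a paragraph of SAP text and a refit in the same package, with no new data. The downsides are a slightly more complex model, reliance on fall 2018 being pre-programme, and a modest gain of uncertain size.
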